10.8. Appendix 8: Endpoint Definitions

Infection and disease definitions for AlloVir prevention trial

- The prevention trial has a primary objective of preventing clinically significant CMV, BKV, EBV, AdV, HHV-6, and/or JCV infection and end-organ disease through Week 14 (~100 days) and a secondary objective of preventing clinically significant CMV, BKV, EBV, AdV, HHV-6, and/or JCV infection and end-organ disease through Week 26 (~6 months).
- The definitions below are intended to assist the Endpoint Adjudication Committee with adjudicating cases of infection and disease, but the committee may also use their judgment to adjudicate cases that are not captured by the definitions below (e.g., rare disease manifestations of the viruses).

Manifestation	Definition
HHV-6	
Clinically significant HHV-6 viremia^{1,2}	
 HHV-6 plasma viral load >10,000 copies/mL on one occasion or >1,000 on ≥ 2 occasions separated by at least a week
HHV-6 encephalitis/post-transplant acute limbic encephalitis³	
 Detection of HHV-6 in the CSF coinciding with acute-onset altered mental status (encephalopathy) or short-term memory loss or seizures AND Other likely infectious or non-infectious causes have been excluded AND ciHHV-6 has been excluded 
OR (if lumbar puncture not possible):
 
 Detection of HHV-6 in the plasma >1,000 copies/mL coinciding with acute-onset altered mental status (encephalopathy) or short-term memory loss or seizures AND MRI findings suggestive of HHV-6 encephalitis such as hyperintensities in the limbic system (abnormalities outside the medial temporal lobes are less common) Other likely infectious or non-infectious causes have been excluded AND ciHHV-6 has been excluded
Other	
 Also consider these manifestations as appropriate: delirium/decreased neurocognitive functioning, acute GVHD, bone marrow suppression, elevated LFTs, idiopathic pulmonary syndrome (in setting of HHV-6 detected from BAL fluid)
BK virus	
Clinically significant BK viremia	
 BK virus plasma viral load >100,000 copies/mL or >10,000 copies/mL on ≥ 2 occasions separated by at least a week
BK virus-associated hemorrhagic cystitis⁵	
 Clinical signs and symptoms of cystitis, including dysuria, lower abdominal pain, and/or other bladder-associated pain or spasms AND Grade ≥ 2 hematuria (per Bedi scale) AND

	
 • BK viruria of >5 log₁₀ copies/mL AND • No other cause for the HC is apparent
Adenovirus	
Clinically significant adenovirus viremia	
 • AdV plasma viral load $>10,000$ copies/mL on a single occasion or $>1,000$ copies/mL and rising, defined as two consecutive results of $>1,000$ copies/mL from the central laboratory, with the second result being higher than the first and drawn at least 48 hours after the first sample.
Adenovirus pneumonia⁶	
 • At least one of the following clinical and/or imaging findings: 
 ○ Suggestive signs or symptoms (cough, dyspnea, tachypnea, hypoxia) ○ CT scan or X-ray with infiltrates suggestive of viral pneumonia (and not a dense lobar consolidation suggestive of bacterial pneumonia or nodule(s) suggestive of fungal pneumonia) AND • AdV identified in BAL, nasopharyngeal swab, sputum, or lung biopsy by PCR, culture, or antigen via IHC methods or clinically significant AdV viremia detected by PCR from plasma (as defined above) AND • No bacterial, fungal, or other probable causative agent identified/cultured
Adenovirus hepatitis⁶	
 • At least one of the following: 
 ○ Serum bilirubin >5xULN or ○ ALT >5xULN or ○ AST >5xULN • AND • Either clinically significant AdV viremia detected by plasma PCR (as defined above) and other causative agents (e.g., other viral causes of hepatitis) and causes (eg, drug-induced, GVHD) ruled out OR • AdV identified via hepatic biopsy via antigen/IHC, or culture
Adenovirus enterocolitis⁶	
 • AdV detected on bowel biopsy via antigen/IHC and culture/PCR AND • EITHER both of the following: 
 ○ Suggestive signs or symptoms (e.g., diarrhea, abdominal pain, ileus, vomiting, GI hemorrhage) AND ○ Endoscopic evidence of lesions (macroscopic or microscopic) not attributed to GVHD

	
OR cytopathic adenoviral effect identified on biopsy
 
OR
 
 • At least 2 suggestive signs or symptoms: diarrhea, abdominal pain, ileus, vomiting, GI hemorrhage AND • AdV isolated from the stool by culture or PCR AND • Other causative agents (e.g., bacterial, viral, amebic) ruled out AND endoscopic evidence of lesions (macroscopic or microscopic) not attributed to GVHD (i.e., biopsy-proven)
Adenovirus pancreatitis⁶	
 • Consistent clinical and imaging findings such as: 
 ◦ Suggestive signs or symptoms (abdominal pain, GI symptoms) ◦ Amylase or lipase >5xULN ◦ Imaging (eg, CT scan) findings suggesting pancreatitis 
AND
 
 • AdV identified by pancreatic biopsy or ERCP brushings/washings via antigen/IHC or culture OR • AdV detected by plasma PCR AND • Other causes (e.g., gallstones, hypertriglyceridemia, parasites, paramyxovirus, other viruses) ruled out
Adenovirus hemorrhagic cystitis	
 • Clinical signs and symptoms of cystitis, including dysuria, lower abdominal pain, and/or other bladder-associated pain or spasms AND 
 • Grade ≥ 2 hematuria (per Bedi scale) AND • AdV viruria of $>5 \log_{10}$ copies/mL AND • No other cause for the HC is apparent
Adenovirus nephritis	
 • At least one of the following: 
 ◦ Suggestive signs or symptoms (impaired renal function, proteinuria, microscopic hematuria, hypertension, dysuria) ◦ Enlarged kidney on imaging ◦ Renal/bladder obstruction AND • AdV identified via renal biopsy via antigen/IHC or culture OR • AdV detected by urine PCR +/- plasma PCR and other causes (e.g., BK virus, JC virus, bacterial and drug-induced) ruled out
Adenovirus encephalitis/myelitis⁶	
 • At least one of the following signs/symptoms of encephalitis: 
 ◦ Abnormal CSF ◦ Focal CNS deficit ◦ Cognitive impairment ◦ Visual symptoms ◦ Seizure ◦ Evidence of compatible lesions by CT scan or MRI

	
AND
 
 • AdV identified in CSF via antigen/IHC, culture, or PCR 
OR (if not possible to perform a lumbar puncture):
 
 • At least two of the following signs/symptoms of encephalitis: 
 ○ Focal CNS deficit ○ Cognitive impairment ○ Visual symptoms ○ Seizure ○ Evidence of lesions by CT scan or MRI AND • AdV detected by plasma PCR AND • Other causes (e.g., JC virus, bacterial, amebic infections and stroke/infarct/CSF leak) ruled out
Adenovirus retinitis/ocular disease⁶	
 • Ophthalmologic exam demonstrating findings consistent with retinitis/ocular disease (eg, retinitis, keratitis, keratoconjunctivitis sicca, iridocyclitis, retinopathy, visual field defects, papilledema, diplopia) and other possible causes (e.g., HIV, CMV, fungal, mycobacterial, bacterial infection, and/or neurologic etiology) ruled out AND • Detection of AdV by PCR from the aqueous or conjunctiva
CMV⁷⁻¹⁸	
Clinically significant CMV viremia	
 • CMV plasma viremia >500 copies/mL on two consecutive results between 1 and 5 days apart
CMV pneumonia	
 • At least one of the following clinical and/or imaging findings: 
 ○ Suggestive signs or symptoms (cough, dyspnea, tachypnea, hypoxia) ○ CT scan or X-ray with infiltrates suggestive of viral pneumonia AND • Detection of CMV in BAL or tissue samples (virus isolation, histopathology, immunohistochemical analysis or in situ hybridization)
CMV GI disease	
 • Signs and/or symptoms of upper and/or lower GI tract involvement (eg, nausea, vomiting, diarrhea) AND • Macroscopic findings on endoscopy AND • Detection of CMV (by culture, histopathology, immunohistochemical analysis or in situ hybridization) in a GI biopsy specimen AND • Other causes (eg, GVHD and AdV) have been excluded
CMV hepatitis	
 • Increased bilirubin and/or increased enzymes AND • No other documented cause of hepatitis AND

	
 • Detection of CMV (by culture, histopathology, immunohistochemical analysis or in situ hybridization) in a liver biopsy specimen • Coinfection with other pathogens like hepatitis C virus may be present without excluding the diagnosis of CMV hepatitis
CMV encephalitis¹⁷	
 • Suggestive signs and/or symptoms (eg, confusion, lethargy, disorientation, seizures) AND • Detection of CMV in a CSF sample (culture or PCR) OR a brain biopsy specimen (culture, histopathology, IHC analysis or in situ hybridization)
CMV retinitis¹⁸	
 • Decreased visual acuity and blurred vision symptoms. Lesions typical of CMV retinitis (eg, small white lesions with intraretinal hemorrhage and vasculitis of nearby retinal vessels, granular necrotizing lesions, post-infectious scars characterized by geographic areas of chorioretinal atrophy with surrounding hyperpigmentation) must be confirmed by an ophthalmologist.
CMV nephritis	
 • CMV infection (by culture, immunohistochemical analysis or in situ hybridization) AND • Histologic features of CMV infection in a renal biopsy specimen (eg, owl's eye intranuclear inclusions, viral particles on electron microscopy) in a patient with renal dysfunction • (Detection of CMV in the urine of a patient with renal dysfunction does not fulfill the definition of CMV nephritis.)
EBV	
Clinically significant EBV viremia	
 • EBV PBMC viral load >10,000 copies/mL on one occasion or >1,000 copies/mL on ≥ 2 occasions separated by at least a week
PTLD (caused by EBV)¹⁹	
 • Suggestive signs and/or symptoms (eg, fever, weight loss, and fatigue; lymphadenopathy with or without compression of surrounding structures; dysfunction of involved organs such as the gastrointestinal tract, lungs, liver, central nervous system, or the allograft) AND • Imaging (eg, CT scan) demonstrating enlarged lymph nodes or a focal mass (Note: PET-CT may be helpful in the evaluation, showing PET-avid lesion, potentially guiding decisions on where to direct biopsies) AND

	
 EBER in situ hybridization from tissue biopsy
EBV meningoencephalitis	
 Neurologic signs and/or symptoms, such as confusion or focal weakness AND Brain MRI with gadolinium with suggestive findings AND EBV detected by CSF PCR
JC virus	
JC viremia²⁰	
 N/A (disregard plasma viral load unless there is evidence of clinical disease)
PML (caused by JC virus)	
 The presence of clinical manifestations and brain imaging findings consistent with PML and not better explained by other disorders AND JC virus detected by PCR from CSF.²¹ Clinical manifestations are diverse but may include behavioral and cognitive abnormalities, motor weakness, gait abnormalities, visual field deficits, speech and language disturbances, incoordination, sensory loss, seizures, headache, and diplopia.²¹ Brain MRI typically shows focal or multifocal white matter lesions, generally without mass effect, that do not conform to vascular territories.²²

HHV-6: human herpes virus 6; ciHHV-6: chromosomally integrated HHV-6; ddPCR: droplet digital polymerase chain reaction; MRI: magnetic resonance imaging; BAL: bronchoalveolar lavage; AdV: adenovirus; HC: hemorrhagic cystitis; IHC: immunohistochemistry; CT: computed tomography; CMV: cytomegalovirus; GVHD: graft versus host disease; ULN: upper limit of normal; ALT: alanine aminotransferase; AST: aspartate aminotransferase; ERCP: endoscopic retrograde cholangiopancreatography; CSF: cerebrospinal fluid; GI: gastrointestinal; CNS: central nervous system; EBV: Epstein-Barr virus; JCV: JC virus; aGVHD: acute GVHD; ECIL: European Conference on Infections in Leukemia; PTLD: post-transplant lymphoproliferative disorder; PET: positron emission tomography; EBER: EBV-encoded RNA; PML: progressive multifocal leukoencephalopathy.

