ⁿ The infection assessment will be performed for all patients who require either treatment for disease or initiation of preemptive therapy during both the primary study period and the follow-up period through Week 26 ([Section 8.3](#)). It is very important to ensure that all procedures, as outlined in the SoA, are performed immediately prior to the initiation of treatment of viral diseases or initiation of preemptive therapy (ie, on the day anti-viral therapy is initiated). Most importantly, a plasma sample for AdV, BKV, CMV, HHV-6, and JCV and a PBMC sample for EBV for PCR testing at the central laboratory should be collected. Patients who develop viral infections will continue to be followed in the study and complete all remaining visits through Week 26.

^o Assessment of quality of life (using FACT-BMT, EQ-5D-5L, EQ-5D-Y, EQ-5D-Y Proxy Version 1questionnaires, as age-appropriate) should be completed prior to any study procedures at this visit.

Table 3: Schedule of Activities – Treatment -- Period 1 for Patients < 12 Years of Age (Week 1 to 14, All Cohorts)

Time Period	Treatment Assignment	Study Drug Administration Day	Treatment Period													
			Wk 1	Wk 2	Wk 3	Wk 4	Wk 5	Wk 6	Wk 7	Wk 8	Wk 9	Wk 10	Wk 11	Wk 12	Wk 13	Wk 14
Study Day		1 ^a	8	14	21	28	35	42	49	56	63	70	77	84	91	98
Visit Window (Days)		NA ^b	±3	±5	±3	±5	±3	±5	±3	±5	±3	±5	±3	±5	±3	±3
Study Procedures																
Review of I/E criteria		X														
Prior & concomitant medications as well as conditioning regimen for HCT			X		X		X		X		X		X		X	
Adverse events ^c		X		X		X		X		X		X		X		X
Physical examination ^d			X		X		X		X		X		X		X	
Weight		X				X				X				X		X
Vital signs ^e		X		X		X		X		X		X		X		X
12-lead ECG ^f		X		X		X		X		X		X		X		X
Clinical labs ^g		X		X		X		X		X		X		X		X
Pregnancy test ^h		X		X		X		X		X		X		X		
BKV, CMV, JCV, and HHV-6 viral load ⁱ			X		X		X		X		X		X		X	

Time Period	Treatment Assignment	Study Drug Administration Day	Treatment Period													
			Wk 1	Wk 2	Wk 3	Wk 4	Wk 5	Wk 6	Wk 7	Wk 8	Wk 9	Wk 10	Wk 11	Wk 12	Wk 13	Wk 14
Study Day		1 ^a	8	14	21	28	35	42	49	56	63	70	77	84	91	98
Visit Window (Days)		NA ^b	±3	±5	±3	±5	±3	±5	±3	±5	±3	±5	±3	±5	±3	±3
Study Procedures																
EBV PBMCs ⁱ		X		X		X		X		X		X		X	X	X
AdV viral load		X	X	X	X	X	X	X	X	X	X	X	X	X	X	X
Treatment Assignment ^j	X															
Virus- Specific T Cell Assessment ^k		X				X		X			X			X		X
Study treatment administration ^l		X		X		X		X		X		X		X		

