^lAll patients will receive infusions of either ALVR105 or placebo. Patients will receive the same [REDACTED] dose for patients ≤40 kg or [REDACTED] dose for patients >40 kg for all infusions of ALVR105, administered at a dose interval of every 14 days (±3 days). Placebo infusions will be administered every other week in order to maintain the blind. As GVHD and CRS are a theoretical safety concern associated with administration of third-party allogeneic T cells, the incidence and severity of GVHD and CRS will be monitored during the study. No patients will be permitted to receive a subsequent infusion of ALVR105 if they develop new onset GVHD Grade >2 or worsening of GVHD (ie, relative to baseline GVHD at the time of enrollment into the study) at the proposed time for infusion of the next dose, or if they develop CRS Grade >2; if any patient develops GVHD or CRS, the Medical Monitor should be contacted immediately, and the patient treated per standard of care. If discontinued for CRS or GVHD these participants should be followed up to resolution of symptoms. Patients may resume treatment only with consultation and agreement between the Medical Monitor and the Investigator. If possible, IVIG and ALVR105 should not be administered on the same day.

^mPatients will be monitored closely and must remain in the clinic for ≥1 hour after the end of each infusion. Vital signs, including body temperature, heart

rate, O₂ saturation, respiration rate, and blood pressure, will be measured at the end of the infusion, and at 15, 30, 45, and 60 minutes after the end of the infusion. Patients must also remain on continuous pulse oximetry for ≥30 minutes after the end of the infusion. Post-infusion monitoring should be completed for all infusions of study treatment.

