8.3. Infection Assessments

Infection assessments will be performed for all patients who, in the opinion of the Investigator, might meet the criteria described in Appendix 8, [Section 10.8](#). It is very important to ensure that all procedures, as outlined in the SoA, are performed for infection assessment immediately prior to the initiation of treatment of viral diseases or initiation of preemptive therapy (ie, on the day anti-viral therapy is initiated).

A symptom checklist should be completed in the infection assessment eCRF.

Patients will continue to be followed in the study and complete all remaining visits through Week 26 as outlined in the SoA.

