8.3.1. Confirmatory Plasma Samples for Suspected Infection

Most importantly, a plasma sample for AdV, BKV, CMV, HHV-6, and JCV, and a PBMC sample for EBV for PCR testing at the central laboratory should be collected. Should confirmatory test results from the central laboratory not be available within the timeframe that the Investigator wishes to initiate anti-viral therapy, the Investigator may use a positive local laboratory test result to make the decision. Whenever it is deemed clinically necessary to use a local laboratory, a plasma sample should also be collected and sent to the central laboratory.

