8.3.2. Samples When Initiating Anti-viral Therapy

If antiviral therapy is to be initiated, it is mandatory to send a plasma sample for AdV, BKV, CMV, HHV-6, and JCV and a PBMC sample for EBV for DNA PCR testing to the central laboratory immediately prior to (ie, on the day of) initiating treatment for AdV, BKV, CMV, EBV, HHV-6, or JCV disease or preemptive therapy in ALL instances. As clinically indicated, stool, urine, and/or CSF samples should be collected for AdV, BKV, CMV, EBV, HHV-6, and JCV and sent to the central laboratory as feasible (see Appendix 8, [Section 10.8.](#))

When local laboratory test results are used for initiating anti-viral therapy, two plasma (and PBMC for EBV) samples for PCR testing must be sent to the central laboratory. The first sample must be collected immediately prior to (ie, on the day of) initiating anti-viral therapy. The second sample must be collected 48-72 hours after initiating anti-viral therapy. The local laboratory result must also be reported in such instances.

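### The only written CMV viremia rule needs two results 1 to 5 days apart, but no two consecutive scheduled on-study CMV samples are that close at any age

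*Protocol*

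**What the plan says.** The protocol's primary endpoint is the proportion of patients with clinically significant infection or end-organ disease from any of six viruses through Week 14, as adjudicated by a blinded committee. Week 26 is a secondary time point. Appendix 8 (Section 10.8) gives the definitions. Its CMV viremia row reads in full: "CMV plasma viremia >500 copies/mL on two consecutive results between 1 and 5 days apart". It has no single-result alternative. The appendix adds that "the committee may also use their judgment to adjudicate cases that are not captured by the definitions below".

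Extra sampling is covered in four places:

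- **Section 8.3:** "Infection assessments will be performed for all patients who, in the opinion of the Investigator, might meet the criteria described in Appendix 8".
- **Schedule of Activities footnote n:** "The infection assessment will be performed for all patients who require either treatment for disease or initiation of preemptive therapy". Section 8.3 and this footnote fix the timing only relative to the start of antiviral therapy.
- **Section 8.3.1 (confirmatory samples):** "Most importantly, a plasma sample for AdV, BKV, CMV, HHV-6, and JCV, and a PBMC sample for EBV" should be collected for the central laboratory. No interval from the first positive sample is stated.
- **Section 8.3.2:** a central sample is mandatory on the day therapy starts. A further condition applies: "When local laboratory test results are used for initiating anti-viral therapy, two plasma (and PBMC for EBV) samples for PCR testing must be sent", and "The second sample must be collected 48-72 hours after initiating anti-viral therapy".

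**The concern.** A rule with a maximum interval can be met routinely only if sampling supplies pairs inside that interval. Here the maximum is 5 days and the shortest scheduled gap is 6.

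The other viruses are treated differently. HHV-6, BKV, AdV and EBV each have a single-result route at a higher threshold. Each also has a repeat route with a minimum interval only (at least a week, or at least 48 hours for AdV). JCV viremia is disregarded without disease. CMV alone has a maximum interval and no single-result route.

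What is at stake is reproducible counting of asymptomatic CMV viremia in the primary composite and its Week 26 counterpart. Two patients with the same viral-load course could be classified differently because one attended a visit early or one site redrew promptly.

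**Working it through.** No figure in the plan needs reproducing. The check takes differences between scheduled sampling days and compares them with the interval of 1 to 5 days.

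**Inputs.** Sampling days come from the Schedule of Activities (Protocol Section 1.3; SAP Appendix 2, Tables 6 to 8). The CMV rows of Protocol Tables 2 and 3 appear shifted in the extracted text, so the SAP copies are used. Protocol Section 2.3.2 confirms alternate-week sampling under age 12.

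**Step 1: nominal gaps (next day minus previous day).**

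| Group | CMV sampling days | Gaps (days) | Gaps of 1–5 days |
|---|---|---|---|
| Age 12 and over | 1, 8, 14, 21, then every 7 to 98 | 7, 6, then 7 twelve times | 0 of 14 |
| Under 12 | 1, 14, 28, 42, 56, 70, 84, 91, 98 | 13, 14 five times, 7, 7 | 0 of 8 |
| Follow-up, all ages | 98, 154, 182 | 56, 28 | 0 of 2 |

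Reading Protocol Table 3 as extracted also gives 0 for under 12 (shortest gap 13 days). The nominal days in SAP Appendix 1 (8, 15, 22 and so on) give a shortest gap of 7 days. The last screening sample and the Day 1 sample can be 1 to 5 days apart, but that pair precedes dosing and bears on baseline status.

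**Step 2: can visit windows alone bring a pair inside 5 days?** Windows are ±3 days at odd weeks, ±5 at even weeks through Week 12, and ±3 at Week 14 and in follow-up. Shortest gap = nominal gap minus both tolerances.

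- Age 12 and over, adjacent weeks: 7 − 3 − 5 = −1, so gaps of 1 to 5 days are possible.
- Under 12, Weeks 2 to 12: 14 − 5 − 5 = 4 by visit windows. These are dosing visits, and footnote l has infusions "administered at a dose interval of every 14 days" with ±3 days. That makes the shortest gap 14 − 3 = 11, so drift cannot supply a pair if the dose interval is kept.
- Under 12, Day 1 to Week 2: 13 − 5 = 8 by visit window alone, so no.
- Weeks 12 to 13 and 13 to 14, both ages: 7 − 5 − 3 = −1 and 7 − 3 − 3 = 1, so possible.
- Follow-up: 56 − 3 − 3 = 50 and 28 − 3 − 3 = 22, so not possible.

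These are limits of what can happen. How often it would happen depends on attendance patterns that the documents do not give.

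**Step 3: other routes to a pair in the visible text.**

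- An unscheduled redraw, permitted as clinically indicated (Section 8.2.2).
- The Section 8.3.1 confirmatory sample, if it happens to be drawn within 5 days.
- The early-termination sample (Section 7.3).
- Local results: the CMV row, unlike the AdV repeat rule, does not require the central laboratory.
- The mandatory day-of-initiation sample, if therapy starts 1 to 5 days after the first positive sample.
- The day-of-initiation sample plus the second sample at 48 to 72 hours. This is 48/24 = 2 to 72/24 = 3 days, inside the rule. It is required only when a local result prompted therapy, and its second value is on treatment.

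**The case against.** The strongest reply is that surveillance gaps are the wrong comparator. A 1 to 5 day rule reads naturally as weekly detection followed by a confirmatory draw. Section 8.3 sends suspected cases to assessment and Section 8.3.1 says a central sample should be taken, so on this view only a cross-reference is missing. Part of this stands: the 8.3.1 sample is a real route, and timing it is an acceptable alternative remedy. But the sample is recommended rather than dated, and 8.3 ties timing to the start of therapy. An untreated patient with viremia therefore has no stated confirmation date.

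Committee judgment also stands as a safeguard, so failing the rule does not mean that a case is necessarily lost. The appendix illustrates that latitude with rare disease manifestations, however. Ordinary viremia sampled on schedule should meet a written rule.

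The visible text is incomplete. Section 8.2.1 shows no text, parts of 8.2.2 are redacted, and the adjudication charter is not available. The SAP describes a Phase 2/3 trial analysed under Amendment 4 with a count endpoint, while this protocol describes Phase 2 with a proportion. The randomized cohorts may therefore be governed by wording not seen here.

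A reader might infer that CMV viremia can never be counted. Step 3 of the working shows otherwise. A reader might also turn the visit windows into percentages of missed events by age. Those would rest on an assumed pattern of drift, with every sample positive and unscheduled samples ignored, and should not be relied on.

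**Conclusion.** The mismatch is real and worth correcting. In the visible text, the written CMV viremia rule is not met by any pair of consecutive on-study samples taken on their nominal days, at any age. Meeting it depends on visit timing, redraws, local testing or the timing of treatment, and otherwise on the committee. Drift cannot help in follow-up, nor under age 12 through Week 12 if the dose interval is kept.

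The conclusion is limited to the committee-adjudicated protocol endpoint and is subject to the charter and redacted text. It does not reach the open-label analysis: SAP Sections 1 and 3.4.1 use investigator-determined infection, including viremia requiring treatment, without the 1 to 5 day rule. A reader might infer bias between arms, but nothing in the documents shows that drift or redraws differ by arm under blinding. The number of events affected and the effect on the primary result cannot be estimated from the documents.

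**What to change.** Reconcile the CMV row of Appendix 8, and the adjudication charter, with the Schedule of Activities:

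- Count two consecutive results above 500 copies/mL at least 1 day apart, scheduled or unscheduled, with no 5-day maximum. This matches the other viruses' repeat rules, and all 14 gaps from age 12 and all 8 under 12 then qualify at their nominal spacing.
- State explicitly whether the Week 14, 22 and 26 samples, nominally 56 and 28 days apart, may form a pair.
- Report the 1 to 5 day rule as a sensitivity analysis.

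If the 1 to 5 day rule is kept as primary, state in Section 8.3.1 that the confirmatory sample already called for is drawn 1 to 5 days after the first CMV sample above 500 copies/mL.

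**Cost.** The first option is a wording change plus one sensitivity analysis, with no extra sampling. Somewhat more CMV events would count, and separate transient episodes may occasionally be paired. The alternative may add a small draw after a first positive sample, which matters for blood volume under age 12.
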